The car following task requires the recruitment of the following attention mechanisms: 1) *processing speed*, used to process and update working memory with task-specific cues (e.g. braking, change of speed) provided by the lead vehicle, 2) *target enhancement*, required to enhance task-specific lead vehicle cues, and 3) *inhibitory control*, required to inhibit the processing of irrelevant environmental information (e.g. other vehicles, pedestrians, etc.).

Visual search task. The visual search task⁸⁷⁻⁹¹ requires participants to search for a target item among multiple distractor items while driving; this task uses displays similar to the search display of the capture task. Search item configurations can be manipulated to evoke either the N2pc or the Pd to measure attentional shifts related to target enhancement or distractor suppression, respectively, during driving performance. This line of research will be the first to examine rapid shifts of attention during driving behavior.

The visual search task requires the recruitment of the following attention mechanisms: 1) *processing speed,* used to process each search item in turn in order to find the target item, 2) *deployment speed,* used to rapidly shift attention towards candidate search items, and 3) *target enhancement,* used to resolve target items from distractor items.

	Specific Aim 1		Specific Aim 2			Specific Aim 3	
Attention	Capture Task	Filtering Task	N2pc	Pd	CDA	Car Following	Visual Search
Mechanism	-	-	-			-	
Processing Speed	Х					Х	Х
Deployment Speed			X	Х			Х
Target Enhancement			X			Х	Х
Distractor				Х			
Suppression							
Inhibitory Control	Х	Х			Х	Х	
Disengagement	Х						
Speed							
Storage Capacity		Х			Х		

Table 2: Summary of attention mechanisms probed in each specific aim Auxiliary Measurements

In addition to the proposed battery, we will administer several neuropsychological exams to determine whether the range of cognitive impairments predominately observed in the breast cancer population are reflected in the HM population. These exams will give us the opportunity to link patterns of cognitive impairment between cancer **populations**. Additionally, we have selected novel measures (circulating inflammatory proteins, retinal anatomy) within the domain of the chemobrain literature to further explore the impact of chemotherapy on the brain and body.

Cognitive assessment. Clinical neuropsychological exams to be used in the current proposal include: *Mini-Mental State Examination*^{5,14,20} (MMSE; mental status, dementia screening tool), *Trails A and* B^{1-4,6-11,15,18,20,22-24,35} (processing speed), *Useful Field of View* (UFOV; processing speed, divided attention, inhibitory control), *Paced Auditory Serial Attention Task*^{18,23} (PASAT; working memory, arithmetic), *Stroop*^{2,3,5-9,12,17,23,24} (executive function).

Vision assessment. Clinical measures of visual deficits to be used include: visual acuity, contrast sensitivity (discrimination threshold for light and dark boundaries), frequency doubler task (visual field deficits), visual function questionnaire (self-reported impairment of visual function), and neuro-ophthalmology supplement (NAS)-10 (self-reported impairment of visual function).

Retinal anatomy. Retinal anatomy is an underutilized tool for studying the link between brain disease and cognitive impairment, particularly in cancer populations. Optical coherence tomography (OCT) provides an easy, non-invasive and reliable method of studying retinal anatomy in healthy and diseased populations. With an axial resolution of 4-6 micrometer, the new generation spectral domain OCT can reliably identify the various neuronal layers of the retina.

Previous work has demonstrated a link between retinal anatomy integrity and neurodegeneration¹¹⁰, particularly in Alzheimer's Disease¹¹¹, Parkinson's Disease¹¹², and Multiple Sclerosis¹¹³. In the current proposal, OCT measurements will allow us to determine the presence of neurodegeneration of the retina in cancer patients receiving chemotherapy, and link declines in retinal anatomy integrity with concurrent declines in cognitive performance. Thus, this method has potential to further develop non-invasive and rapid imaging biomarkers for chemotherapy-related cognitive impairment.

Cirrus HD-OCT (Carl Zeiss Meditec Inc.) will be used to obtain scans of the retina and optic nerve. Specifically, the Macular Cube and the Optic disc cube scans will be performed at each visit. These scans can be performed without the need for pupillary dilation and takes about 2 minutes per eye. The relevant parameters obtained with the optic nerve scan includes the *retinal nerve fiber layer thickness* (global average, quadrant average and clock hour average). The macular cube scans will provide the *ganglion cell/inner plexiform layer thickness* (global average and sector average) and *macular thickness*.

Given the link between retinal anatomy and neurodegeneration, which has direct implications for cognitive impairment, OCT will be measured for all three groups across the three study visits in the following manner: HM groups will undergo OCT measurement at all three study visits; given that we anticipate minimal variability in healthy participants across a three-month time period, a randomly sampled subset of healthy controls (n=10) will undergo OCT across all three study visits. This measurement protocol will allow us to control for any within-subject variability in retinal anatomy that may be observed across groups so that we can account for concurrent variability in cognitive performance.

Circulatory Inflammatory Proteins. Circulatory levels of cytokine interleukin (IL) proteins and C-Reactive Proteins (CRPs) have been found to negatively affect brain function. Specifically, increased levels of IL proteins⁹²⁻⁹⁷ and CRPs¹¹⁶⁻¹¹⁸ have both been associated with impairments of memory and executive function, and has been implicated as a potential mechanism for chemotherapy-related cognitive impairment^{114,115}. Given tumor presence and chemotherapy treatment associated with increased levels of these proteins in the blood⁹⁸⁻¹⁰⁰, measurement of inflammatory protein levels is essential to further understand the link between cancer, chemotherapy, and cognitive impairment.

Given the link between inflammatory protein concentration levels and cognitive impairment, CRP concentrations will be measured for all three groups at all three study visits; this measurement protocol will allow us to control for any within-subject variability in CRP concentration levels that may be observed across groups so that we can account for concurrent variability in cognitive performance.

Section 6.0 Measurement of Effect:

Cognitive Battery

□ Response time (Capture Task) and response accuracy (Filtering Task) Electrophysiology

□ Amplitude and latency of N2pc, Pd, and CDA electrophysiological components Driving Simulation

- Response time (Visual Search Task)
- Brake time, mean following distance, and number of incursions (Car Following Task)
 CRP
 - Concentration levels of circulating inflammatory proteins

OCT

Surface area and volume of retinal ganglion cell layer and optic nerve fiber

Given that we are not proposing an intervention trial our primary outcome measures will not be related to the progression of HM.

Section 7.0 Study Parameters:

Summary of Study Events and Durations. Each study visit is anticipated to take approximately 2.5 hours to complete. Table 1 contains a summary for the schedule of study events to occur at each research component. Study induction takes place at the beginning of Visit 1. Time requirements for research participants at each study event are as follows:

- □ Study Induction (~.5 total hours):
 - Informed consent (20 minutes)
 - Demographic Information (10 minutes)
 - Comorbidity Index (conducted offline)
 - Anemia Evaluation (conducted offline
- □ Each Study Visit (~2.5 total hours):
 - Cognitive Battery (40 minutes)
 - Electrophysiology (15 minutes)
 - Driving Simulation (20 minutes)
 - Neuropsychological Exams (45 minutes)
 - Health & Mobility Questionnaires (10 minutes)
 - OCT (10 minutes)
 - Blood Collection (10 minutes)

	Pre- Induction	Study Induction	Visit 1 (Month 0)	Visit 2 (After Month 1 or 1 treatment	Visit 3 (After Month 3 or 3 treatment
				cycle)	cycles)
HM Diagnosis	X				
Control Group ID	X				
Informed Consent		Х			
Demographic Information		Х			
Comorbidity Index		Х			
Anemia Evaluation		Х			
Chemotherapy Treatment			X	X	X
Cognitive Battery			X	Х	Х
Electrophysiology			X	Х	X
Driving Simulation			X	Х	Х
Neuropsychological Exams			X	X	X
Health & Mobility Questionnaires			X	X	X

OCT		Х	Х	X
Blood Collection/ Protein Assay		Х	X	X

Section 8.0 Drug Formulation and Procurement:

This pilot study is not a pharmaceutical trial.

Section 9.0 Toxicity and Adverse Event Reporting Guidelines:

This research has been classified as Minimal Risk.

There is the potential to detect cognitive impairment in research participants during cognitive assessment. After consent, if a participant receives an MMSE score of 20 or less, they will be discontinued from the study. If cognitive impairment is identified, research personnel will proceed in the following way. First, the participant will be informed that an unexpected finding was encountered that may have clinical significance, and that the clinical significance is best determined in conjunction with his or her primary care physician. Next, research personnel will ask the participant for their permission to contact their primary care physician to help facilitate follow-up to determine clinical significance. The primary care physician will then be contacted and provided clinical context and concerns sufficient to allow for subsequent evaluation, workup, and treatment of any unexpected finding. If the participant refuses to have the research personnel directly contact their physician, the research personnel will offer the participant a written explanation that an abnormal neurological finding was encountered and the written material will include encouragement to have an evaluation, as well as a phone number of the Mind and Brain Health Labs to contact with questions or in case they change their mind.

Section 10.0 Statistical Considerations:

Our primary goal is to examine the effects of chemotherapy on behavioral and electrophysiological measures of cognitive ability in an understudied cancer population. To this end, analyses for the proposed pilot project will be performed on three groups: healthy controls (no cancer, no chemotherapy), very-low to intermediate risk HM patients receiving supportive care treatment (no chemotherapy), and intermediate to very-high risk HM patients receiving chemotherapy treatment.

Statistical Power. Although many of the statistical analyses will involve complex modeling procedures, the main emphasis of our aims and hypotheses is to determine differences between groups and pre-post treatment. Hence, the issue of statistical power can be addressed via consideration of the magnitude of standardized effect sizes that can be detected with reasonable probability. The current study aims to collect pilot data and demonstrate protocol feasibility for future studies and funding opportunities. As such, we plan to obtain 15 samples per group for a total sample size of 45.

While we realize we will not have sufficient power to declare smaller effects statistically significant, as this is a pilot study, it will allow us to estimate effect sizes for a number of outcomes to conduct fully powered studies. In future large-scale confirmatory studies, with a sample size of 32 per group, we will have 80% power to detect a standardized effect size of 0.65 (a medium to large effect) for within group changes, and an effect size of .9 for between group differences. These power calculations assume a two-tailed alpha of 0.01 to informally adjust for multiple comparisons and multiple testing. A standardized effect size of 0.65 corresponds to a 10% difference in response time from healthy controls (mean=1394.75, standard deviation = 213.23). This sample size will allow adequate power to detect medium to large effects within group, and large effects between groups.

Statistical Analysis. To assess the data collected, for each group, we will first produce frequency tables, calculate descriptive statistics, and create univariate graphs (e.g. box-plots, histograms) on the

predictor and response variables to investigate distributional properties and check for outliers in the data. Although the specific statistical models that we will use to test our formal hypotheses and to calculate confidence intervals will depend on the outcome distributions that we observe in our data, we anticipate using linear mixed models and generalized linear mixed models, as appropriate. This modeling approach allows us to properly account for the distribution of the outcome measure while also properly modeling repeated effects and adjusting for potentially confounding variables. Confidence intervals of all effects will be calculated in order to assess clinical significance of statistical results.

We will employ linear mixed models and general linear models to **assess** within-subject, betweensubject, and mixed effects of:

- Behavior:
 - Capture condition, stimulus ISI, and treatment group on response time measures in the Capture Task
 - Filtering condition, storage load, and treatment group on response accuracy measures in the Filtering Task
- Driving simulation:
 - Treatment group on response time measures in the Visual Search Task
 - Treatment group on lead car distance variability, brake time, and number of incursions during the Car Following Task
- □ Electrophysiology:
 - Capture condition, stimulus ISI, and treatment group on Pd (amplitude, latency) and N2pc (amplitude, latency) measures during the Capture Task of the Attention Battery
 - Filtering condition, storage load, and treatment group on N2pc (amplitude, latency) and CDA (amplitude) measures during the Filtering Task of the Attention Battery
 - Treatment group on N2pc (amplitude, latency) and Pd (amplitude, latency) measures during the Visual Search Task of the Driving Simulation

Our primary hypothesis is that chemotherapy treatment negatively affects core neural mechanisms of attention. Here, we present predictions for how chemotherapy would affect outcome measures from each task and electrophysiological measure, where specific predictions are given based on how impairments in different attention mechanisms would affect the pattern of data observed in each task.

Attention Measures

Capture task. Two dissociable mechanisms of attention are measured in this task. First, *inhibitory control* is required to suppress the processing of the capture display; inhibitory control mechanisms will be tracked by the Pd component. Second, *disengagement speed* is required to rapidly release attention from capture displays to prepare for the subsequent search display; disengagement mechanisms will be tracked by the N2pc component. There are three possible predictions for impairments in each attention measured in the capture task.

- Hypothesis 1: Inhibition effect/No disengagement effect. Relative to comparison subjects, this hypothesis predicts a chemotherapy-related: 1) increase in response time differences between contingent and singleton capture conditions, 2) increase in Pd amplitude, and 3) decrease in N2pc amplitude.
- Hypothesis 2: No inhibition effect, disengagement effect. Relative to comparison subjects, this hypothesis predicts a chemotherapy-related: 1) increase in response times in both capture conditions, 2) decrease in N2pc amplitude, and 3) no difference in Pd amplitude.

Hypothesis 3: Inhibition effect, disengagement effect. Relative to comparison subjects, this hypothesis predicts a chemotherapy-related: 1) increase in response times in both capture conditions, 2) increase in response time differences between contingent and singleton capture conditions, 3) increase in Pd amplitude, and 4) decrease in N2pc amplitude.

Filtering task. Two dissociable mechanisms of attention are measured in this task. First, *inhibitory control* is required to suppress the encoding of distractor items; inhibitory control mechanisms will be tracked by both the N2pc and CDA electrophysiological components. Second, sufficient *storage capacity* is required to maintain multiple items in working memory during the delay period; storage capacity will be tracked by the CDA electrophysiological component. There are three possible predictions for impairments in each attention mechanism measured in the filtering task.

- Hypothesis 1: Capacity effect, no inhibitory control effect. Relative to comparison subjects, this hypothesis predicts a chemotherapy-related: 1) decrease in response accuracy in both storage and filtering conditions, 2) decrease in CDA amplitude, and 3) no difference in N2pc amplitude.
- Hypothesis 2: No capacity effect, inhibitory control effect. Relative to comparison subjects, this hypothesis predicts a chemotherapy-related: 1) decrease in response accuracy only in the filter condition, 2) increase in N2pc amplitude, and 3) increase in CDA amplitude.
- Hypothesis 3: Capacity effect, inhibitory control effect. Relative to comparison subjects, this hypothesis predicts a chemotherapy-related: 1) increase in response accuracy differences between filtering and storage conditions, 2) increase in N2pc amplitude, and 3) increase in CDA amplitude.

Car following task. According to the hypothesis that chemotherapy treatment impairs *processing speed*, a chemotherapy-related decline should be observed in car-following performance because fewer resources would be available for processing lead vehicle events. Specifically, delayed processing would lead to delayed updating of lead vehicle driving information, which would lead to greater variability in car-driver distance and longer delay in driver brake onset, where longer brake delays would lead to more crashes.

Visual search task. According to the hypothesis that chemotherapy treatment impairs *deployment* speed, a chemotherapy-related increase in response time should be observed because attentional resources will be slower to deploy; furthermore, changes in the complexity of the driving environment (e.g. road hazards, high visual load) would lead to longer response times as a function of complexity because attentional resources would be more engaged with more complex environments, leading to poorer *inhibitory control*. For electrophysiology, this hypothesis predicts chemotherapy-related reductions in N2pc amplitude and increases in N2pc latency – because lower inhibitory control would lead to a lower probability of being prepared to deploy attention towards the task-relevant search display.

Auxiliary Measures

Cognitive assessment. According to the hypothesis that chemotherapy impairs attention mechanisms, we predict impairments in performance across neuropsychological exams within the cognitive assessment, because these tests measure cognitive abilities directly related to attention. For example, memory tests (e.g. CVLT, BVRT) require attention to successfully encode information into memory storage; failures of attention would lead to failures of encoding into memory, and thus impairments in memory retrieval.

Vision assessment and retinal anatomy. Our hypothesis is that chemotherapy negatively affects higher-level attention mechanisms, such that attention impairments cannot be explained by impairments in low-level visual processes. Therefore, we predict no changes across vision assessment exams and questionnaires. Conversely, given the hypothesis that chemotherapy leads to morphological changes in

neural structures, and the fact that the retina is a neural structure, we do predict reductions in retinal and optic nerve thickness.

C-Reactive Proteins. According to previous work, circulatory levels of C-Reactive Proteins (CRPs) increase in response to inflammation, including tumor genesis and growth. We therefore predict an increase in CRP levels in HM patients relative to healthy controls; furthermore, we predict further increase in CRP levels in HM patients receiving chemotherapy relative to HM patients receive best supportive care treatment. Finally, we hypothesis that increases in CRP levels will predict concurrent increases in attention impairment both within and between research participants.

Section 11.0 Records to be Kept:

The following forms will be collected during each study visit, and stored in locked filing cabinets within keycard restricted lab space in the Mind and Brain Health Labs (first floor of Clarkson Doctor Building North). Data collection forms will be entered electronically into a study database on a password-protected, encrypted, dedicated research network.

- Phone Screen Script
- Patient Tracker
- Demographic Form
- □ MMSE Data Collection Form
- □ HM Data Collection Form
- □ Hematopoietic Cell Transplant Co-Morbidity Index (HCT-CI)
- Beck Depression Index
- □ Life Space Questionnaire
- □ Medication Form
- □ Health Survey
- □ Visual Function Questionnaire
- □ Far Visual Acuity Form
- □ Contrast Sensitivity Form
- □ Frequency Doubler Task (FDT) Record Sheet
- □ Trails A Data Collection Form
- □ Trails B Data Collection Form
- □ Stroop Test Participant Form
- □ Stroop Test Scoring Form
- □ PASAT Scoring Sheet
- □ UFOV Scoring Sheet

In addition to the forms indicated above, electronic records of performance during the cognitive, electrophysiological, and simulation batteries will be maintained in their raw form on password protected computers. After completing each testing battery, raw data will be stored on a password-protected, encrypted, dedicated research network.

Section 12.0 Patient Consent: The consent form must adhere to the guidelines established by the Institutional Review Board of the University of Nebraska Medical Center.

Section 13.0 References

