Finally, previous studies have used measures with high experimental control and low external validity, providing limited insight into how chemotherapy-related cognitive impairment translates to real-world behavior. It is essential to understand how chemotherapy affects real-world behaviors that could have a profound impact on public health, as impairments in these activities could lead to incursions with the general population. Importantly, identifying which aspects of real-world behaviors are affected by chemotherapy could lead to the development of targeted rehabilitation strategies, ultimately leading to improved cognitive health and quality of life. Thus, combining basic and translational research into future studies will provide better insights into how the lives of chemotherapy patients – and the lives of those in their surroundings – are affected on a daily basis.

Section 3.0 Eligibility Criteria:

Inclusion criteria for HM patients include: 1) HM diagnosis, 2) scheduled to receive treatment based on risk classification, 3) between 19 to 80 years of age, and 4) normal or corrected-to-normal vision. Inclusion criteria for healthy controls will be that they are matched to patient demographics.

Exclusion criteria for HM patients include the presence of: 1) second cancer diagnosis in addition to recent HM diagnosis (however, patients with localized skin cancer may not be excluded), 2) prior radiation or chemotherapy treatment, 3) cognitive impairment (MMSE score <25) prior to baseline assessment, 4) patients who are critically ill or require urgent initiation of chemotherapy will be excluded from this study, 5) patients with any other condition that may not allow safe participation in the study based on the clinical judgment of the treating oncologist will be excluded. Exclusion criteria for healthy controls include HM cancer diagnosis in addition to all exclusion criteria for HM patients. There is the potential to detect cognitive impairment in research participants during cognitive assessment. After

Section 4.0 Registration Procedure:

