Patients will be recruited through the Department of Internal Medicine, Division of Hematology-Oncology with the assistance of Drs. [name], [name], [name], [name], [name], [name], [name], [name], [name], and [name]. Recently diagnosed HM patients will contact – or be contacted by – new patient coordinators to schedule a clinical visit at UNMC. During initial scheduling with new patient coordinators, patient contact information will be recorded in a Patient Tracker, and they will be informed that research is being conducted to study cognitive abilities in HM patients. A brief description of the study will be included in their new patient packet. At the time of their clinical visit, Drs. [name], [name], [name], [name], [name], [name], [name], [name], [name], and [name] will provide further information about the study, and ask patients if they are interested in participating. Interested patients will be screened for inclusion/exclusion criteria, provided with informed consent during their clinical visit, and their demographic information will be collected after consenting to participating in the study. After their clinical visit, a member of the Mind & Brain Health Laboratory (MBHL) will contact consented patients to schedule their initial pre- treatment research study visit. MBHL lab personnel will coordinate with patient case managers to determine their next treatment date so that subsequent study visits can be scheduled accordingly.

Demographically matched healthy controls will be recruited from the MBHL registry and RedCap (#564-10-EP: Building UNMC-based research programs focused on wellness, frailty, and aging) registry based on demographic information collected from HM patients who have already been inducted into the study. Specifically, healthy controls will be matched to HM patients along the dimensions of age (\pm 5 years), gender (same gender), race (same race), and education (\pm 2 years). These registries provide query options for search for specific demographic factors, and are comprised of individuals who have expressed interest in participating in research studies. In addition, spouses or caregivers of chemotherapy patients may be recruited as healthy controls to examine the psychosocial effects of caring for chemotherapy patients on cognitive abilities.

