Given the limited availability for enrollment of HM patients into this study, potential research patients will not be selected based on demographic factors of gender and race. Nevertheless, equal preference will be given to individuals across all gender and race categories.

Research participants that have been recruited into the study will be undergo study induction either in the Division of Hematology/Oncology (HM patients) or in the Mind and Brain Health Labs (healthy controls). After study induction, all research participants will undergo the same testing battery within the Department of Neurological Sciences at each study visit. HM patients will complete each testing battery prior to undergoing their chemotherapy treatment scheduled on the same day.

Research participants will receive monetary compensation (\$20/hour) for their participation. In the event that adequate funding is not secured for compensation, research participants will be recruited as volunteers.

Section 5.0 Treatment Plan of Research Design:

Experimental Design

Patients will be recruited from one of two targeted treatment groups, based on their risk stratification: 1) high risk group for examining the influence of chemotherapy on cognitive impairment; and 2) low risk supportive care treatment schedules, which represents the chemotherapy control group. Additionally, we will recruit a demographically matched (matched at age, gender, and educational status) healthy control group, which will serve as the cancer and chemotherapy control group.

Participants will complete a three-month longitudinal study that will examine the parametric effects of HM-specific chemotherapy treatments on cognitive and electrophysiological measures of attention

mechanisms. We will sample during intervals corresponding to the onset of treatment cycles, thus giving us the opportunity to examine additive dose-response effects of chemotherapy treatment. Sampling intervals for chemotherapy patients (or control patients) will occur according to the following schedule: 1) after HM diagnosis but prior to receiving chemotherapy treatment, providing a baseline assessment, 2) one month after baseline assessment or after one treatment cycle (whichever comes first), 3) three months after baseline assessment after three treatment cycles (whichever comes first).

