Experimental Control Measures. There are several health factors that may be affected by HM disease and treatment that could potentially impact cognitive performance independent of chemotherapy treatment per se. To mitigate these potential confounds, we will measure these factors across patients and controls to include as cofactors during the modeling procedure of our analysis. If there is a link between factors unrelated to chemotherapy and variability in cognitive performance across groups, we will include these additional cofactors in the final model to control for these confounds; if there is no link between factors unrelated to chemotherapy and variability in cognitive performance, we will not include these factors in the final model to control for these confounds; if there is no link between factors unrelated to chemotherapy and variability in cognitive performance, we will not include these factors in the final model.

Experimental control measures will include:

- Disease Comorbidity. Patients may have other diseases in addition to the HM diagnosis critical to the current proposal. Hematopoietic cell transplantation-comorbidity index (HCT-CI) is a tool commonly utilized in the transplant setting that measures multiple organ impairments across 17 different categories of organ dysfunction. Results from the HCT-CI are summated into a single total score, which will serve as a baseline measurement of disease comorbidity. Patients without any known or suspected cardiac or pulmonary diseases will be considered to have normal echocardiogram and pulmonary function test during calculation of HCT-CI.
- Anemia. HM patients will likely suffer from anemia that could result in fatigue. To control for anemia-related fatigue on cognitive ability, we will measure blood cell counts in patients and control participants. Blood cell counts will be collected from HM patients' most recent clinical visits. For healthy controls, we will obtain blood cell counts from their most recent clinical visit as well, though this measure may not be as recent as that of an HM patient; given that we do not anticipate these levels changing significantly in the healthy population, larger variability in the difference between blood and cognitive testing will not impose any limitation on our experimental design.

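### Section 3.0 sets a vision requirement for both HM patient groups but none for healthy controls, which could narrow unadjusted cross-sectional HM-versus-healthy differences

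*Combined protocol and SAP*

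**What the plan says.** Section 3.0 closes the patient inclusion list with "3) between 19 to 80 years of age, and 4) normal or corrected-to-normal vision". The list covers all HM patients, so it applies to both the chemotherapy and the supportive-care group.

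For the third group the same section says: "Inclusion criteria for healthy controls will be that they are matched to patient demographics". It then adds: "Exclusion criteria for healthy controls include HM cancer diagnosis in addition to all exclusion criteria for HM patients". Section 4.0 defines the match: "healthy controls will be matched to HM patients along the dimensions of age" (within 5 years), gender, race and education (within 2 years).

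Vision is measured during the study. The auxiliary measurements in Section 5.0 state: "Clinical measures of visual deficits to be used include: visual acuity, contrast sensitivity", followed by a visual-field task and two questionnaires. Section 4.0 says that "all research participants will undergo the same testing battery within the Department of Neurological Sciences at each study visit". For health factors that might affect cognition apart from chemotherapy, Section 5.0 says "we will measure these factors across patients and controls to include as cofactors during the modeling procedure of our analysis". It keeps a factor in the final model only if it proves to be linked to performance. The measures listed there are the comorbidity index, blood counts, and questionnaires on depression, medication, health and life space.

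**The concern.** The groups enter under different visual standards, yet they are compared on tasks that depend on sight. The capture and filtering tasks present visual displays. The N2pc, Pd and CDA are defined by which visual field is attended, ignored or remembered. Visual search and car following need sight as well, although driving also draws on other abilities.

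Controls are age-matched to patients who may be as old as 80, so some controls will probably be older adults. If some of them have poor uncorrected vision, the healthy reference is worse than it would be under the patients' standard: response times are longer and accuracy is lower. In a comparison at a single visit, a real post-treatment deficit in HM patients could look smaller. A real pre-treatment difference could be hidden, which would appear to support the part of H1a and H2a that predicts no difference at baseline. The pilot is meant to supply effect sizes for later studies (Section 10.0), so a distorted estimate would be carried forward.

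**Working it through.** **Reading the eligibility text.**

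- Patient inclusion: diagnosis, scheduled treatment, age, vision.
- Control inclusion: demographic match only. None of the four matching factors is visual.
- Exclusions inherited by controls: second cancer; prior radiation or chemotherapy; MMSE below 25; critical illness or urgent chemotherapy; a condition that makes participation unsafe in the treating oncologist's judgment. None concerns vision. Because vision is an inclusion item for patients, the rule that carries over exclusions does not bring it across.
- Vision tests in Section 5.0: no threshold for entry or analysis.
- Adjustment: vision tests are not among the experimental control measures. Section 10.0 mentions confounder adjustment in general terms and does not name vision.

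As written, then, a control with poor vision is eligible, and no rule says how that control is handled in the analysis.

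**The plan's own figures.** The only power statement (Section 10.0) is for a future study with 32 per group, 80% power and two-sided alpha 0.01. The noncentral t distribution gives a required n of 31.01 (so 32) for the within-group effect of 0.65, and 30.5 (so 31) for the between-group effect of 0.9. The response-time conversion also holds: 0.10 × 1394.75 / 213.23 = 0.654. None of these figures is disputed.

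**Possible size of the shift.** The documents give 15 controls and a healthy-control SD of 213.23. They give neither the frequency of poor vision nor its effect on performance. Assume k = 1 to 3 impaired controls, each performing δ = 0.5 to 1.0 SD worse.

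- Shift in the control mean = k × δ / 15.
- Low end: 1 × 0.5 / 15 = 0.033 SD, or 0.033 × 213.23 ≈ 7 response-time units (the plan states no unit).
- High end: 3 × 1.0 / 15 = 0.20 SD, or 0.20 × 213.23 ≈ 43 units.
- Standard error of a two-group difference at 15 per group = √(1/15 + 1/15) = √(2/15) = 0.365 SD.
- Shift relative to that standard error: 0.033 / 0.365 = 0.09 to 0.20 / 0.365 = 0.55.

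**Effect on an estimated effect size.** Take the plan's between-group value of 0.9 as the true difference. With p = k/15, the control variance becomes 1 + p(1 − p)δ², and the observed value is (0.9 − shift) / pooled SD.

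- Low end: control variance 1.016, pooled SD √1.008 = 1.004, observed value 0.867 / 1.004 = 0.86.
- High end: control variance 1.16, pooled SD √1.08 = 1.039, observed value 0.70 / 1.039 = 0.67.

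**Change from baseline.** If poor vision adds a constant b to a control's score at every visit, the change is (Y3 + b) − (Y1 + b) = Y3 − Y1. A stable additive deficit drops out, so the figures above apply only to unadjusted comparisons at one visit.

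**The case against.** The strongest reply is that the gap is small and partly covered.

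- **Vision is recorded in controls.** They take the same battery, and Section 11.0 lists acuity, contrast sensitivity and visual-field forms at each visit. An impaired control could be identified at Visit 1. This stands, but identification has no stated consequence.
- **Adjustment is permitted.** Section 10.0 allows for confounders and checks outliers, and it predicts no change on the vision tests. This also stands, but permission is not a rule, and the prediction is an assumption that the plan leaves open to challenge in the one group not screened for vision.
- **The safety exclusion might catch severe cases.** It concerns safe participation rather than task performance, and it rests on a treating oncologist, whom a healthy control would not ordinarily have.
- **The design blunts the effect.** Section 10.0 puts weight on pre-post change as well as on group differences. Contingent minus singleton, filtering versus storage, and contralateral versus ipsilateral are within-person contrasts that partly remove a general visual deficit. This stands and limits the point.

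A reader might infer three stronger things that the documents do not support. First, that the estimated effect of chemotherapy is compromised: both HM groups meet the same vision criterion, and Section 5.0 makes supportive-care patients the chemotherapy control, so that contrast is untouched. Second, that every HM-versus-healthy contrast is biased towards no impairment: change scores largely escape. For EEG amplitudes the direction is also uncertain, because Section 10.0 predicts increases under some hypotheses and decreases under others, and the plan does not say how poor vision moves each component. Third, that visually impaired controls will in fact be enrolled: Section 11.0 lists a phone screen script whose content is not in the documents, and it may ask about vision.

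**Conclusion.** The difference in entry standards is in the current text and is worth correcting. Its consequence is conditional and limited to unadjusted cross-sectional comparisons of HM patients with healthy controls on visually based tasks and EEG measures, including those in H1a and H2a.

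The size cannot be derived from the documents. The range of 0.03 to 0.20 SD depends wholly on the assumed number of impaired controls and the assumed deficit, and even its upper end is about half of one standard error at the pilot's sample size. This is a cheap improvement to the plan, not a flaw that threatens its main conclusions. It does not change the stated sample sizes.

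**What to change.** In Section 3.0, add "normal or corrected-to-normal vision" to the healthy-control inclusion criteria, checked with the acuity test already in the battery. In Section 10.0, add a sensitivity analysis that repeats the HM-versus-healthy contrasts with baseline acuity or contrast sensitivity as a covariate.

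The cost is one line of eligibility text and one extra analysis of data already collected, with no new procedure. The downside is that a few registry volunteers would be passed over.
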